To evaluate avoidance of clinically significant migration

To evaluate the mucosal appearance (integrity of the anchoring site) and the integrity of the anastomosis after the device retrieval.

To assess the patient acceptance and tolerability of the device, during the Colovac Device implantation period

To assess the anastomosis at 6 and 12 months post-surgery.

To assess the integrity of the anchoring site at 6 and 12 months post-surgery

STUDY ENDPOINTS

PRIMARY SAFETY ENDPOINT

The primary safety endpoint is the rate of subjects with post-operative major complications within 12 months.

Major complications are defined as:

Index surgery-related, device-related (including implantation and retrieval), or ostomy-related (including creation and reversal) **and** Clavien-Dindo Severity³²:

Grade II and re-admission to hospital is required for additional treatment* **or**

Grade III, IV or V

OR

- Patient safety risk leading to failure to reverse the stoma within 12 months**

*Additional treatment does not include administration of antiemetics, antipyretics, analgesics, diuretics and electrolytes and hospital stay does not include emergency room visits.

**Does not include failure to reverse stoma for reasons unrelated to patient safety.

The definition of major complications is intended to select only complications that do not respond to less complex treatments such as dietary change and administration of nominal drugs (antiemetics, antipyretics, analgesics, diuretics and electrolytes).

For example, a Grade II anastomotic complication, may be managed with prolongation of hospitalization or an emergency room visit for close monitoring or administration of antibiotics, and should not be considered a major complication. However, a Grade II complication that is recalcitrant to outpatient or emergency room treatment and requires re-hospitalization for administration of non-nominal drugs or other treatments, should rightly be considered a major complication.

As shown in Table 1, no Grade I and all Grades III, IV and V complications are major complications. Further, the only Grade II complications that are major complications are one that cannot be adequately treated in a clinic or emergency room and instead require re-admission to the hospital for administration of non-nominal drugs or other treatments.

Table 1: Explanation of Major Complications

Clavien-Dindo Severity	Explanation	Major Complication?

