Parastomal Hernia/ Hernia at the ileostomy site	Resulted in a prolongation of the index hospitalization. Required conservative management	Grade I	No
	Resulted in an emergency room visit without re-admission to the hospital	Grade I or II	No
	Resulted in a re-admission to the hospital. Required conservative management	Grade I	No

Adverse Event	Treatment	Clavien-Dindo Severity	Major Complication?
	Resulted in a re-admission to the hospital. Required reoperation	Grade IIIa or IIIb	Yes

¹Nominal drugs: antiemetics, antipyretics, analgesics, diuretics and electrolytes

Additionally, the CEC will verify that major complications with Grade II severity are eligible for inclusion as major complications based on the additional requirements. Similarly, the CEC will verify that failure to reverse the stoma within 12 months was based on an adverse event or other patient safety concern rather than patient preference or other reason unrelated to patient safety.

The Clavien-Dindo severity classification, the basis for the severity stratifications of the complications, is included in Section 0. Adverse events will also be classified by seriousness based on the definition provided below in Section 0.

Note that all adverse events will be collected and presented in the clinical study report. To provide a fair comparison of the two treatment pathways, the following planned procedures for both pathways will not be considered a safety event within the Primary Safety Endpoint:

- Stoma reversal surgery
- Endoscopic Colovac retrieval
- Stoma creation surgery for incomplete anastomotic healing

However, all AEs related to these procedures that meet the criteria for Major Complications will be included in the Primary Safety Endpoint analysis. These procedures are summarized below in Figure 14.

[figure not shown]

Figure 14: Description of Procedures and Alignment to the Primary Safety Endpoint

PRIMARY EFFECTIVENESS ENDPOINT FOR COLOVAC ARM

The primary effectiveness endpoint assessed for all subjects in the Colovac arm at 12 months is a clinically meaningful reduction in stoma creation rate.

Avoidance of stoma creation is an objective, standardized primary effectiveness endpoint that ensures that all cases (whether a result of the procedure, the device or the patient's poor healing) of failure to divert the fecal stream, anastomotic leak, and migration that resulted in a stoma conversion are counted as endpoint failures.

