The endpoint will be considered a failure if the subject requires stoma creation. This endpoint addresses the following:

Diversion of the fecal stream from the anastomosis site:

Failure to divert the fecal stream from the anastomosis (whether a result of the procedure, the device, or the patient's poor healing) which results in stoma creation within 12 months of the index surgery will be counted as endpoint failures.

In addition, all anastomotic leaks (ALs) (including incomplete healing at Day 10 not related to failure to divert the fecal stream) that result in stoma creation for any reason within 12 months of the index surgery and will be counted as endpoint failures

Device migration

All device migrations that result in stoma creation will be counted as endpoint failures.

Primary Effectiveness Endpoint Success

To be considered a primary effectiveness success, the subject must have no stoma creation, regardless of the reason, within 12 Months of the index surgery. Note: Fecal contamination which results in stoma creation within 12 months of the index surgery (whether a result of the procedure, the device or the patient's poor healing) will be counted as endpoint failures.

PERFORMANCE GOAL FOR PRIMARY EFFECTIVENESS

Study success will be defined as a clinically meaningful stoma reduction rate in the Colovac patients AND statistical non-inferiority on the primary safety endpoint (Colovac vs. Control). A benefit-risk assessment of all the clinical data will be performed to determine the ostomy reduction rate that balances the risk that device use may pose. This ostomy reduction rate will be considered clinically meaningful and provide the basis for the actual performance goal for this endpoint. Details of the benefit-risk assessment are provided in Section 0.

SECONDARY AND EXPLORATORY ENDPOINTS

Secondary Effectiveness Endpoints

For Comparison between the Colovac and Control Arms

- Cumulative Length of Hospital Stay through 12 Months post-discharge: Total length of hospital stay (in days) through the 12-month visit will be compared between the two study arms.

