The composite effectiveness endpoint for the Colovac-treated patients is a measure of subject-level success that will be assessed on all subjects in the Colovac arm who have the device implanted until Day 10. Additionally, all subjects who have the device removed before Day 10 due to a device-related reason will be included in the assessment as failures. Subjects who have the device removed before Day 10 due to a non-device related reason will be included in the assessment as missing.

Diversion of fecal stream from the anastomosis will be confirmed using the Boston Bowel Preparation Scale (BBPS) score (BBPS = 3). To standardize this assessment, photographs of the anastomosis site will be taken during the endoscopic procedure following device removal and the review of the endoscopic photographs will be entrusted to the Clinical Evaluation Committee for independent review of the presence of feces using the Boston Bowel Preparation Score (BBPS). A BBPS \neq 3 will be considered a failure.

ALs classified as ISREC severe Grade B and Grade C will be considered clinically significant and symptomatic. The ISREC grades are defined in Section 6.3.5.

Clinically significant migration is defined as movement of device that allows fecal contents to reach the anastomosis site evidenced by:

Migration of entire stent below the Sacral Promontory as indicated by fluctuation in the length of the sheath that extends out of the anus and confirmed by radiographic displacement, with or without subject symptoms or clinical findings suggestive of anastomotic leak (pain, fever, elevated CRP, elevated WBC); or

Expulsion of the device.

If the entire stent is below the sacral promontory, the physician should consider converting the patient to the standard of care ostomy within 24 hours.

A treatment algorithm flowchart detailing the treatment pathways is provided below in Figure 15.

[figure not shown]

Figure 15: : Colovac Treatment Algorithm Flowchart

Figure 16 illustrates the decision pathways for determination of the secondary composite effectiveness endpoint.

[figure not shown]

Figure 16: Secondary Composite Effectiveness Endpoint Determination

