- IVa	single organ dysfunction (including dialysis)
- IVb	Multi organ dysfunction
Grade V	Death of a patient

As shown in Table 5, by definition, all ISREC Grade A ALs are CL Grade 0 or I severity, all ISREC Grade B ALs are CL Grade II or IIIa severity, and all ISREC Grade C AL are CL Grade IIIb, IVa, IVb or V in severity. Consistent with the definition of major complications, the CL Grade II is divided into those with and without re-hospitalization.

All ISREC Grade B ALs that are CL Grade II severity with re-hospitalization or CL Grade IIIa severity, and all ISREC Grade C ALs (CL Grades IIIb, IVa, IVb and V severity) will be considered CSS AL. The only ISREC Grade B ALs that would be excluded from the CSS AL definition would be those that are CL Grade II severity without re-hospitalization.

Table 5: Assessment of CSS AL

ISREC AL Grade	CL Severity Grade	CSS AL?
Grade A	0, I	No

ISREC AL Grade	CL Severity Grade	CSS AL?
Grade B	II without re-hospitalization	No
	II with re-hospitalization	Yes
	IIIa	Yes
Grade C	IIIb, IVa, IVb, V	Yes

All ALs will be reported as adverse events and rates will be compared between the Colovac and Control groups. Grade B ALs that require re-hospitalization and/or require non-pharmaceutical treatment are considered “severe.”

Severe Grade B and Grade C AEs will be considered clinically significant and symptomatic.

To determine device relatedness of clinically significant and symptomatic AL, assessments will be performed at the time of intervention and device removal to determine if the device was effective at diverting the fecal stream (non-device related removal) or not (device-related removal).

Device relatedness for AL will be determined using the same diversion of fecal matter and migration criteria as the primary effectiveness endpoint:

Diversion of fecal stream from the anastomosis site confirmed by absence of feces at the anastomosis site confirmed by endoscopic evaluation between the sheath and the colonic wall performed before the device is removed (i.e. BBPS=3); AND
Absence of clinically significant migration

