Grade II	Requiring pharmacological treatment with drugs other than such allowed for grade I complications. Blood transfusions and total parenteral nutrition also included.
Grade III	Requiring surgical, endoscopic or radiological intervention
- IIIa	Intervention not under general anesthesia
- IIIb	Intervention under general anesthesia
Grade IV	Life-threatening complication (including CNS complications)* requiring IC/ICU-management
- IVa	single organ dysfunction (including dialysis)
- IVb	Multi organ dysfunction
Grade V	Death of a patient

*brain hemorrhage, ischemic stroke, subarachnoidal bleeding, but excluding transient ischemic attacks (TIA),
Intermediate care: IC; ICU: Intensive care unit.

The following information will also be collected:

- Seriousness using the SAE definition in Section 0.
- Action taken
- Date of resolution
- Outcome

All adverse events will be followed until the event is resolved or stabilized and/or deemed permanent. An independent Clinical Evaluation Committee (CEC) will be responsible for adjudicating the severity, seriousness and relatedness of the adverse events. The adjudication decision of the CEC is the final

event decision and the one which will be used for the AE analyses. The CEC responsibilities are discussed in Section 0.

A Data Safety Monitoring Board (DSMB) will monitor the safety of the investigational device, the progress of the clinical investigation and the critical performance endpoints. The DSMB responsibilities are discussed in Section 0.

If the AE meets the criteria for an SAE, the investigator must send the completed AE form by email or fax to the sponsor within 3 days.

In all cases, the sponsor notifies the FDA, National Competent Authorities (NCAs), Notified Bodies (NBs) and the Institutional Review Boards (IRBs)/Ethics Committees (ECs) of the SAE, if required. For all SAEs, the sponsor classifies the event as expected/unexpected using the list of anticipated adverse events provided in the labeling.

The sponsor will send an updated MDCG 2020-10/2 “Clinical Investigation Summary Safety Report Form” to the National Competent Authorities (NCAs) of the EU member states each time a new reportable event or a new finding to an already reported event is to be reported as per the MDR 2017/745 reporting requirements.

CLINICAL EVALUATION COMMITTEE

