The primary effectiveness endpoint for the Colovac-treated patients is: A clinically meaningful reduction in stoma creation rate

PRIMARY SAFETY ANALYSIS

The primary safety hypothesis is that the proportion of subjects with post-operative major complications within 12 months in the Investigational group is non-inferior to the proportion in the Control group using a 10% margin of non-inferiority. The hypotheses are as follows:

Definitions:

p_I : Proportion of subjects with postop major complications in the Investigational group.

p_C : Proportion of subjects with postop major complications in the Control group.

For the specified constant, $0 < \delta < 1$, the hypotheses of non-inferiority are:

$$H_0: p_I - p_C > \delta \text{ vs. } H_A: p_I - p_C \leq \delta.$$

The test will be based on the upper bound of a one-sided 95% confidence interval for the difference in proportions, Investigational minus Control. A conclusion of non-inferiority is supported if the upper bound of the confidence interval is <0.10 .

Non-inferiority Margin

This margin of $\delta=0.10$ is an appropriate value for the non-inferiority margin because the expected major complication rate in this study is approximately 40% for the Colovac group, and 48% for the Control group. As these rates have nearly the highest variance in the binomial distribution, use of a 10% margin is a reasonable choice per Chow and Song³⁹. This article mentions a “classical method” of determining the non-inferiority margin. As an example of a NI margin for a binary response (e.g. a success or failure rate), this method indicates that as a general rule, if the success rate is between 50% and 80% (failure rate between 20% and 50%), then a non-inferiority margin or equivalence limit of up to 20% could be chosen for non-inferiority trials. Although the expected major complication rate is approximately 40%, 10% was selected as a more conservative margin.

PRIMARY EFFICACY ANALYSIS

Study success will be defined as a clinically meaningful stoma reduction rate in the Colovac patients AND statistical non-inferiority on the primary safety endpoint (Colovac vs. Control). A benefit-risk assessment of all the clinical data will be performed to determine the ostomy reduction rate that balances the risk that device use may pose. This ostomy reduction rate will be considered clinically meaningful and provide the basis for the actual performance goal for this endpoint.

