The Safety Population will include all subjects randomized in the study who receive the study treatment, i.e. Colovac or Standard of Care. Subjects will be analyzed according to the treatment actually received. If a subject received Colovac for any duration, the subject will be analyzed in the Colovac treatment group. Otherwise the subject will be included in the Standard of Care group. The Safety Population will be used for all safety-related analyses. This population will be used in the primary safety analysis and missing primary outcome data will not be imputed. All subjects who have the device removed before Day 10 due to a device-related reason will be included in the assessment as failures.

INTENTION TO TREAT POPULATION

All randomized subjects comprise the ITT population and will be tracked. Subjects will be analyzed according to the randomized treatment assignment. This population will be used in the primary efficacy analysis. All subjects who have the device removed and require conversion to ostomy will be included in the assessment as failures. Any missing primary outcome data will be imputed using multiple imputation techniques.

The ITT population will also be used in all other efficacy analyses, without imputation for missing data.

PER PROTOCOL POPULATION

The per-protocol dataset is a subset of subjects who are included in the ITT dataset. Subjects who have major study deviations (i.e., those who do not meet the inclusion/exclusion criteria, those who receive a treatment other than one of the study treatments, or those having other study deviations that could potentially affect clinical outcomes) will be excluded from this dataset. The CEC will determine which study deviations are major.

The per-protocol population will only be used for the analysis of the primary endpoints as a sensitivity analysis.

STATISTICAL METHOD AND ANALYSIS

For general data summary, the number of subjects with data, mean, standard deviation, median, minimum and maximum will be presented for continuous data. Frequency and percentage will be presented for categorical data.

SECONDARY EFFECTIVENESS ANALYSIS

To limit the overall type I error rate to 2-sided 0.05 for the secondary effectiveness endpoints, a gated hierarchical testing approach will be adopted. Four of the secondary effectiveness endpoints will be tested in the order presented below, and as follows:

Cumulative hospital stay post-discharge

Comprehensive Classification Index (CCI)

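### The Safety Population paragraph scores device-related removals before Day 10 as failures, although the primary safety endpoint has no removal criterion; the sentence probably belongs to the Day-10 composite

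*Combined protocol and SAP*

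**What the plan says.** Section 8.5.1 (Safety Population) says that this population serves the primary safety analysis and that missing primary outcomes are not imputed there. The next sentence reads: "All subjects who have the device removed before Day 10 due to a device-related reason will be included in the assessment as failures". It does not say which assessment is meant.

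The endpoint is defined elsewhere without any reference to removal:

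- Primary Safety Endpoint section: "The primary safety endpoint is the rate of subjects with post-operative major complications within 12 months". A major complication must be related to the index surgery, the device or the ostomy, and be either Clavien-Dindo Grade II with re-admission for additional treatment or Grade III to V. Failure to reverse the stoma by 12 months for patient-safety reasons also counts.
- Section 8.1.1: the Colovac parameter in the hypothesis is "Proportion of subjects with postop major complications in the Investigational group".
- Primary Safety Endpoint section, after Table 3: "the following planned procedures for both pathways will not be considered a safety event within the Primary Safety Endpoint". The list is stoma reversal surgery, endoscopic Colovac retrieval, and stoma creation for incomplete anastomotic healing. Adverse events from these procedures count only if they meet the major-complication criteria.

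Under the secondary Day-10 composite the plan says: "Additionally, all subjects who have the device removed before Day 10 due to a device-related reason will be included in the assessment as failures". A companion rule there treats non-device-related early removals as missing. Section 8.5.2 assigns the other efficacy analyses, and hence the composite, to the ITT population.

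**The concern.** The only specific analysis that the Safety Population paragraph names is the primary safety analysis, so a literal reader would apply the failure rule to it. That would put an event outside the endpoint definition into a co-primary endpoint. It could do so in one arm only, because control subjects have no device to remove. The Colovac failure rate could then only rise, at the expense of power for non-inferiority. The same proportions would also feed the sample-size re-estimation in section 8.10.

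**Working it through.** **Which endpoint the sentence fits.**

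- *Primary safety* (12 months, major complications): no removal criterion, and failure is not a term of the endpoint.
- *Primary effectiveness*: to succeed, "the subject must have no stoma creation, regardless of the reason, within 12 Months of the index surgery". Removal without a stoma is not a failure.
- *Day-10 composite*: the time horizon, the subject-level success/failure scoring and the wording all match.

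The composite is the natural home. That the sentence was carried over from there is an inference.

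**Who would be added.** Only Colovac subjects with a device-related removal before Day 10 and no major complication by 12 months.

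- The exemption list covers stoma creation for incomplete healing. It does not list stoma creation after migration or device failure.
- Clavien-Dindo Grade III is "Requiring surgical, endoscopic or radiological intervention", and IIIb is intervention under general anesthesia. The Risk to Benefit Rationale describes stoma creation as surgery under general anesthesia. Such a conversion would therefore probably be Grade IIIb and already count.
- In SAFE-1 all 3 of 15 migrations came with leakage and were managed by ostomy creation.

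This suggests few or no net additions. SAFE-1 cannot settle it, because it used an earlier device and a 14-day implant and its major complications are not itemised. Even if its net addition was 0/15, the exact 95% upper limit is 1 − 0.025^(1/15) = 21.8%.

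**Inputs for the illustration.** Colovac 40%, Control 48%, margin 0.10, 342 randomized 1:1, 7% loss to follow-up, 90% power (section 8.4); one-sided 95% bound (section 8.1.1). Evaluable per arm: 171 × 0.93 = 159.

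**The plan's own figure.** Fixed-sample normal approximation, unpooled variance:

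n per arm = (z₁₋α + z₀.₉₀)² × (0.40×0.60 + 0.48×0.52) / (0.10 + 0.08)²

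- One-sided 0.025: (1.960 + 1.282)² × 0.4896 / 0.0324 = 158.8, so 159 per arm. 318 / 0.93 = 341.9, so 342, which matches.
- One-sided 0.05: (1.645 + 1.282)² × 0.4896 / 0.0324 = 129.4, so 130 per arm. 260 / 0.93 = 279.6, so 280, which does not match.

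The plan attributes 342 to simulation of its adaptive design, which cannot be rerun from the text. Both levels are shown below for that reason.

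**Effect of k net-added Colovac failures.** With p_I = 0.40 + k/159:

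power = Φ{ [0.10 − (p_I − 0.48)] / √[(p_I(1−p_I) + 0.48×0.52)/159] − z₁₋α }

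| k | p_I | Power, one-sided 0.05 | Power, one-sided 0.025 |
|---|---|---|---|
| 0 | 40.0% | 94.5% | 90.0% |
| 3 | 41.9% | 89.4% | 82.5% |

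For k = 3 the standard error is 0.0557 and 0.1611 / 0.0557 = 2.89. Subtracting 1.645 or 1.960 gives the two powers.

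**Direction of the error.** Take a true 10-point excess (Colovac 58%) and add 3 points, so that p_I = 0.61. The standard error is 0.0554, and Φ(−0.03/0.0554 − 1.645) = 1.4%. Without the addition it is 5%. False non-inferiority falls.

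**Interim.** With 140 / 2 = 70 per arm, one added subject moves the Colovac rate by 1/70 = 1.4 points. The standard error of the difference is √(0.4896/70) = 8.4 points, so sampling noise dominates.

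**The case against.** The strongest reply is that the endpoint is not in doubt. Its definition and the hypothesis statement agree, and the CEC's adjudication is final for adverse-event analyses. One unlabelled sentence in a population paragraph does not redefine it. This largely stands, and it is a good reason to call the point minor. It does not remove the contradiction, because the sentence directly follows the naming of the primary safety analysis.

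Other readings are possible but fit less well:

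- *A missing-data clarification.* The sentence follows the no-imputation rule, but it covers all removed subjects, not only those with missing outcomes.
- *The efficacy sensitivity analysis on the Safety population (section 8.7).* Section 8.5.1 does not mention it, and its endpoint is stoma creation.
- *A deliberate conservative safety rule.* This cannot be excluded. The endpoint definition and planning rate would then have to state it.

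A reader might also infer that the plan leaves open how an unplanned early retrieval is scored for safety. The available text does not support that, because Figure 14 (procedures and the safety endpoint) and Figure 17 (Colovac leaks by grade and device relationship) are not shown and may settle it.

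Finally, the power figures rest on no documented early-removal rate, and the 94.5% baseline differs from the plan's 90%. Both objections are fair, and the figures are only an illustration.

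**Conclusion.** The sentence in section 8.5.1 conflicts with the definition of the primary safety endpoint and is probably a carry-over from the Day-10 composite. The point holds as a minor one.

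Its size depends on how many device-related early removals are not already major complications. That number is probably small and may be zero. The conclusion that it is small assumes that stoma creation after migration or device failure would be graded IIIb, and that SAFE-2 removals resemble those in SAFE-1. The power figures also assume the planning rates and a fixed-sample approximation.

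A reader might infer that the trial is likely to be underpowered, or that the safety conclusion could be biased in favour of the device. The documents support neither. No early-removal rate is given from which to predict a power loss, and the rule can only count against Colovac.

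**What to change.** Move the sentence out of the Safety Population paragraph and keep it with the Day-10 composite, analysed in the ITT population. State that the primary safety analysis counts only CEC-adjudicated major complications as defined in the Primary Safety Endpoint section. Tabulate device-related early removals separately, and label any analysis that counts them as safety failures a sensitivity analysis.

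If the sponsor does intend the rule for safety, reconcile section 8.5.1 with the endpoint definition and the list of exempt procedures, and reflect it in the 40% planning rate.

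The cost is one sentence moved, one clarification and one table, with no new data. The downside is that the primary safety rate loses a possibly deliberate conservative element, which the table keeps visible.
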